4.12 Timeline

00-06 months: development of protocol, submission for research ethics approval, submission of PhD proposal
06-09 months: establishment of trial centres
09-27 months: recruitment
09-21 months: evaluation of design
27-30 months: delivery of research protocol completed for final recruits
30-36 months: final analyses and write-up

5. Regulatory and ethical considerations

5.1 Regulatory framework

This study is a randomised trial of fortified or unfortified HDM versus PTF to supplement MOM. The fortifier used is multicomponent breast milk fortifier which is classified as a food supplement for special medical purposes and is not an investigational medicinal product, and as such is not subject to the Medicines for Human Use (Clinical Trials) Regulations 2004. This study is registered with the clinicaltrials.gov online registry and results database.

5.2 Ethical approval and monitoring

The study protocol, patient information sheet and consent form will be submitted to the Research Ethics Committee for approval and subsequently to the R&D department of Chelsea and Westminster Hospital for site specific approval. As part of the ethics approval process, this study has been extensively peer reviewed by reviewers as outlined in the peer review process by the Joint Research Compliance Office, Imperial College London. As part of the PhD, the progression of the study and PhD will be assessed by the Progress Review Panel, department of medicine, Imperial College London.

5.3 Adverse Events

As this study is simply comparing standard feeding practices, there will be no expected adverse events related to the study. However, we are required by the sponsor to include the following information:

ADVERSE EVENTS

DEFINITIONS

Adverse Event (AE): any untoward medical occurrence in a patient or clinical study subject.

Serious Adverse Event (SAE): any untoward and unexpected medical occurrence or effect that:

? Results in death

? Is life-threatening – refers to an event in which the subject was at risk of death at the time of the event; it does not refer to an event which hypothetically might have caused death if it were more severe

- Requires hospitalisation, or prolongation of existing inpatients' hospitalisation

? Results in persistent or significant disability or incapacity

? Is a congenital anomaly or birth defect

Medical judgement should be exercised in deciding whether an AE is serious in other situations. Important AEs that are not immediately life-threatening or do not result in death or hospitalisation but may jeopardise the subject or may require intervention to prevent one of the other outcomes listed in the definition above, should also be considered serious.

REPORTING PROCEDURES

All adverse events should be reported. Depending on the nature of the event the reporting procedures below should be followed. Any questions concerning adverse event reporting should be directed to the Chief Investigator in the first instance.

Non serious AEs

All such events, whether expected or not, should be recorded.

Serious AEs

An SAE form should be completed and faxed to the Chief Investigator within 24 hours. However, relapse and death due to conditions associated with prematurity and hospitalisations for elective treatment of a pre-existing condition do not need reporting as SAEs.

All SAEs should be reported to the Fulham Research and Ethics Committee where in the opinion of the Chief Investigator, the event was:

? 'related', ie resulted from the administration of any of the research procedures; and
? 'unexpected', ie an event that is not listed in the protocol as an expected occurrence
Reports of related and unexpected SAEs should be submitted within 15 days of the Chief Investigator becoming aware of the event, using the NRES SAE form for non-IMP studies. The Chief Investigator must also notify the Sponsor of all SAEs.

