4.7 Withdrawals and protocol violations

4.7.1 Temporary discontinuation of feeds/alternative feeds

Infants in the trial may develop feed intolerance or suspected/confirmed necrotising enterocolitis (NEC) requiring the cessation of enteral feeds. The period of no feeding may vary from a few hours to a number of days. Once feeding is re-established, the infant will continue with the allocated interventional arm. However, there may be circumstances in which continuation of the allocated feed is deemed inappropriate by the clinical team. Examples would include feed intolerance and the use of hydrolysed or elemental feeds. Infants would remain in the study and included in the "intention-to-treat analysis."

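### Section 5.3 builds unexpectedness into the SAE definition, so serious but anticipated events have no assured 24-hour form or sponsor notification

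*Combined protocol and SAP*

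**What the plan says.** Section 5.3 defines an adverse event (AE) without any condition on expectedness: "any untoward medical occurrence in a patient or clinical study subject". Its definition of a serious adverse event (SAE) adds one: "any untoward and unexpected medical occurrence or effect that" satisfies a seriousness criterion, such as a threat to life or a longer hospital stay.

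The reporting rules open with a general statement, "All adverse events should be reported", and then give two procedures according to the nature of the event:

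- **Non-serious AEs:** "All such events, whether expected or not, should be recorded".
- **Serious AEs:** a form goes to the Chief Investigator within 24 hours, and the Chief Investigator tells the sponsor of every SAE. Some events are exempt: "relapse and death due to conditions associated with prematurity and hospitalisations for elective treatment of a pre-existing condition do not need reporting as SAEs".

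SAEs go on to the ethics committee only if they are both related and unexpected. Here, and only here, the protocol explains what unexpected means: "an event that is not listed in the protocol as an expected occurrence". Section 5.3 contains no such list. It says that "there will be no expected adverse events related to the study".

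Elsewhere, section 4.7.1 says: "Infants in the trial may develop feed intolerance or suspected/confirmed necrotising enterocolitis (NEC) requiring the cessation of enteral feeds". Section 4.9.6 has suspected or confirmed NEC and culture-positive bloodstream infection recorded weekly until discharge from the unit. Section 4.9.1 retrieves both from the national database for all randomised babies.

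**The concern.** Seriousness and expectedness are separate properties of an event. Seriousness should decide whether an event is handled as an SAE; expectedness should decide, with relatedness, who else must hear of it. Section 5.3 merges the two at the definition and then applies expectedness a second time at the ethics committee step.

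The practical stake is speed and oversight. The 24-hour clock and the sponsor's right to be told both hang on the word SAE. NEC and bloodstream infection are the short-term outcomes that the planned multicentre trial is meant to address (sections 1 and 2.1), so they are the serious events of most interest here. They are also events that neonatal staff may well see as anticipated in babies of this gestation. If staff take that view, the literal definition lets them leave the SAE form unsent.

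**Working it through.** No arithmetic applies. The check is to cross the two properties and see which rule in section 5.3 covers each combination.

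1. **Not serious, unexpected:** covered by the non-serious procedure.
2. **Not serious, expected:** covered by the non-serious procedure, which says that expectedness does not matter.
3. **Serious, unexpected:** an SAE, unless exempt. Form within 24 hours, sponsor notified, ethics committee told if also related.
4. **Serious, expected:** not an SAE on the literal definition, and not non-serious on the listed criteria. Only the general statement that all AEs are reported applies. No named procedure, clock or sponsor notice attaches to it.

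One combination of the four is therefore left without a named procedure.

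**Redundancy.** On the written definition, every SAE is serious and unexpected. The ethics committee set is then serious, unexpected and related, and unexpected again. The second test removes nothing. It has work to do only if an SAE can also be expected, so the definition and the procedure do not fit together.

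**Where a first non-fatal NEC episode falls**, if it meets a seriousness criterion:

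- *Reading A.* Apply the explanation given in the ethics committee rule. NEC is not on a list of expected occurrences, because section 5.3 has no list. NEC is unexpected, so the episode is an SAE and gets the 24-hour form and sponsor notice.
- *Reading B.* Take section 4.7.1 as showing that the protocol anticipates NEC. The episode is then expected and fails the SAE definition. It remains a reportable AE and is recorded as study data, but the 24-hour form and sponsor notice are not required.

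The exemptions do not settle the choice. They concern relapse, death and elective admissions, and a first non-fatal episode is none of these.

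**Effect of removing the condition from the definition.** SAEs become all serious events that are not exempt. The ethics committee set becomes serious, related and unexpected, which is the same set as before. Only the 24-hour form and sponsor notice widen, to take in combination 4.

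**The case against.** The strongest reply is that section 5.3, read as a whole, already lets seriousness govern. The clause on medical judgement treats important AEs that may jeopardise the infant as serious, with no mention of expectedness. The exemption for deaths from complications of prematurity would be largely unnecessary if anticipated complications were already outside the definition. The only stated meaning of unexpected points to Reading A. All of this has force: Reading A is arguably the better reading. It does not close the gap. The judgement clause says which AEs count as serious in other situations and does not take the expectedness condition out of the SAE definition. The explanation of unexpected sits in the ethics committee rule, not beside the definition.

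Four stronger inferences might tempt a reader, and the documents do not support them.

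- *That such events have no reporting route at all.* They remain AEs under "All adverse events should be reported", and NEC and bloodstream infection are captured under sections 4.9.1 and 4.9.6. What those sections provide is data capture, with no 24-hour clock or sponsor notice, so they do not replace the expedited route.
- *That sections 4.7.1 and 5.3 contradict each other on NEC.* Section 5.3 speaks of events related to the study; section 4.7.1 says that NEC may occur, without attributing it to the study. Both can be true.
- *That NEC is definitely excluded from SAE reporting.* That needs Reading B, which treats a passage about interrupting feeds as if it classified adverse events.
- *That a comparison between arms is distorted.* Feeding is unblinded (section 4.6), so classification could in principle differ by arm, but nothing shows that it would. Section 4.11.2 plans no analysis of SAE counts, and NEC and infection are captured independently of SAE forms.

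**Conclusion.** The point holds in a limited form. The SAE definition wrongly includes expectedness, this makes the later filter redundant, and on one defensible reading serious anticipated events miss the 24-hour form and sponsor notification. It is a defect in the safety reporting rule. The validity of the trial's comparisons is not in question.

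Its size cannot be put as a number. The documents give no rate of serious non-fatal NEC for this population, and how many episodes would go unreported as SAEs depends on which reading staff adopt. The same rule applies in all three arms.

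The conclusion rests on two assumptions: that staff apply the definition as written, and that at least some would regard NEC as anticipated. A portion of text immediately after these procedures was not in the copy reviewed, so no claim is made about what may stand there.

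**What to change.** Delete the words *and unexpected* from the SAE definition in section 5.3, so that seriousness alone defines an SAE. Keep relatedness and unexpectedness only as the filter for ethics committee reports, as the section already does.

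The cost is a two-word edit and some additional SAE forms and sponsor notices for serious anticipated events. As shown above, the set of events that goes to the ethics committee does not change, and no planned efficacy analysis is affected. The edit does not decide whether NEC counts as unexpected for ethics committee reports. That question exists now and would remain unless the protocol also listed the events it regards as expected.

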5.4 Indemnity

Imperial College London holds negligent harm and non-negligent harm insurance policies which apply to this study/ Imperial College Healthcare NHS Trust holds standard NHS Hospital Indemnity and insurance cover with NHS Litigation Authority for NHS Trusts in England, which apply to this study

5.5 Sponsor

Imperial College London will act as the main Sponsor for this study. Delegated responsibilities will be assigned to the NHS trusts taking part in this study.

5.6 Funding

This study will be funded through CI core budget while grant funding is being sought.

5.7 Audit

The study may be subject to inspection and audit by Imperial College London under their remit as sponsor and other regulatory bodies to ensure adherence to GCP and the NHS Research Governance Framework for Health and Social Care (2nd edition).

5.8 Study Management

The day to day management of the study will be co-ordinated through the section of Neonatal Medicine, Imperial College London.

5.9 Publication Policy

Results of the study will be disseminated by publication in peer reviewed scientific journals, internal report, and conference presentation. All parents of participants will be sent a report of the study findings in the form of a letter. This will be sent to them once all data have been collected, analysed and the findings have been written up. A copy of the main publication will be provided to all study investigators. Investigators will be encouraged to share results with participants' parents as well.

